Unanticipated problem (UP). any incident, experience, or outcome that meets all of the following criteria: unexpected, in terms of nature, severity, or frequency, given (a) the research procedures that are described in the protocol-related documents, such as the IRB-approved research protocol and informed consent document; and (b) the characteristics of the study population; related or possibly related to participation in the research (in this guidance document, possibly related means there is a reasonable possibility that the incident, experience, or outcome may have been caused by the procedures involved in the research);

PROTOCOL TITLE: Care to Plan: Preliminary Efficacy of a Tailored Resource for Family Members of Persons with Dementia

and suggests that the research places participants or others at a greater risk of harm (including physical, psychological, economic, or social harm) than was previously known or recognized.

Phase II participants will be asked at 3 and 6 month follow up: “In the last three months, since your last survey, was there any new or worsening health problem that caused you to be unable to perform your daily routine (i.e. not go to work or volunteer), seek medical care (i.e. go see your doctor, go to the ER or hospital), or take a new medication?” Those medical events will be documented as adverse events. Other events that will also be considered adverse events are included below.

All AEs (following consent) will be collected on an adverse event form, in electronic format. AEs experienced by a participant during a study procedure (i.e. intervention/survey) will be reported within 5 days of discovery to the University of Minnesota IRB (per the University’s IRB procedures) and annually to the NIA in data monitoring reports.

AE that occur outside of the context of a study procedure (i.e. intervention/survey), as well as those that are determined to be not related to the participant’s involvement in the study, will be documented via the team’s electronic AE form and included in the annual report (to be shared with IRB, Safety Officer, and NIA Program Officer).

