 - Medical events or emergencies: Research staff will call 911 as needed for emergencies (if during study procedure) or provide psychological support and encourage the participant to follow-up with their medical provider as needed (if occurred outside of study procedures). These medical issues (unrelated to study involvement) are considered expected, due to the nature of our study population. These events will be documented/reported as adverse events per above protocol if they meet one of the following criteria: a new or worsening health problem that causes the participant to 1) be unable to perform their daily routine, 2) seek medical care (provider visit, hospitalization, residential care placement, etc.), or 3) take a new medication. *[Note: Medical events or emergencies of a non-participant will not be considered/document as adverse events].*
 - Death of participant is reported promptly to the University of Minnesota IRB per above procedures (and is also reported to the Safety Officer and NIA within 24 hours of the team's knowledge if determined potentially related to study involvement; otherwise is included on routine annual reports shared with Safety Officer and NIA). Deaths in our study population (unrelated to study involvement), are considered expected. *[Note: Deaths of a non-participant will not be considered/document as adverse events].*
 - Suicidal ideation of participant: If participant informs study staff of thoughts of suicide, staff will discuss the concern with the participant and offer resources (i.e. [name] line, healthcare provider, etc.). Staff will ask them to provide verbal agreement not to harm themselves, and alert PI immediately. If necessary, staff will call 911. This will be documented/reported as serious adverse event.
 - Abuse/Neglect of participant: Document as adverse event per above protocol. If indicated, make vulnerable adult report to adult protective services.
 - Other events that in the discretion of the PI should be reported as adverse events.
- Not considered adverse events:

PROTOCOL TITLE: Care to Plan: Preliminary Efficacy of a Tailored Resource for Family Members of Persons with Dementia

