- If a participant scores 16 or higher on the CES-D [risk for depression], study staff will provide resources as needed (i.e. <https://www.samhsa.gov/>, healthcare provider, and Riverside/Senior Care Navigation). Mental health concerns are common in our study population and fluctuation of assessment scores is expected. Unless participant indicates a concern regarding self-harm or that the health issue has caused them to: be unable to perform their daily routine, seek medical care, or take a new medication, it will not be documented as an adverse event.
- Survey responses indicating changes in sleep, stress/anxiety, activities of daily living, or general well-being alone will not trigger an adverse event report. These concerns are common in our study population and fluctuation of assessment scores is expected. Unless participant indicates a concern regarding self-harm or that the health issue has caused them to: be unable to perform their daily routine, seek medical care, or take a new medication, it will not be documented as an adverse event.
- Routine or planned medical encounters for symptoms or conditions that are not new, worsened, or changed since enrollment, as well as those events that have not caused the participant to: be unable to perform their daily routine, seek medical care, or take a new medication, will not be documented as an adverse event.
- A physical attack or injury to participant by a non-participant (i.e. care recipient) would be documented/reported as an adverse event if the participant requires medical care. *[Note: Other potential dementia related behaviors that do not result in participant injury are not considered adverse events.]*
- Participant reports that non-participant (i.e. care recipient or person with memory impairment) displays risk-behavior (i.e. aggression/threats, comments about death or self-harm): This will not be documented as adverse event, as individual is not enrolled in the study. If participant reports concern to study staff, study staff will encourage them to follow up with healthcare provider or Riverside/Senior Care Navigation for resources.
- Suicidal ideation of non-participant (care recipient): If participant shares concern about care recipient (non-participant) suicidal ideation, study staff will talk about the concern and provide resources as requested (i.e. [name] line, healthcare provider, etc.). This is not documented as an adverse event, as individual is not enrolled in the study.

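### The injury-by-care-recipient item in Section 18.1.2 names only medical care as a trigger for adverse event status, so it classifies some injuries differently from the general three-trigger rule

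*Combined protocol and SAP*

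**What the plan says.** All the relevant text is in Section 18.1.2 of the protocol, printed under Section 19.0.

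- **Scripted question.** Phase II participants are asked at 3 and 6 months about "any new or worsening health problem that caused you to be unable to perform your daily routine", or that led them to seek medical care or take a new medication. The protocol then states: "Those medical events will be documented as adverse events".
- **General rule for medical events, in the list of events that count as AEs.** Such events "will be documented/reported as adverse events per above protocol if they meet one of the following criteria". The criteria are "a new or worsening health problem that causes the participant to 1) be unable to perform their daily routine, 2) seek medical care" (with examples of care), "or 3) take a new medication".
- **Injury item, in the list headed "Not considered adverse events".** A physical attack on or injury to the participant by a non-participant, such as the care recipient, "would be documented/reported as an adverse event if the participant requires medical care". A note adds that other dementia-related behaviors without injury to the participant are not AEs.
- **Neighboring items.** The three items just before the injury item, on the CES-D score, on survey responses and on routine medical encounters, each keep all three triggers as the route back to AE status.

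**The concern.** The general rule and the scripted question depend on the consequence for the caregiver, whatever the cause. The injury item singles out one cause and names one consequence. Because it sits in a list of events that are not AEs, its condition reads naturally as the only exception. The two triggers left out are those kept by the three items before it, and no reason is given.

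The protocol itself introduces these scenarios as ones that may arise because of the study population. AEs go into the annual report to the IRB, the Safety Officer and the NIA Program Officer. If two staff members can classify the same injury differently by relying on different items, the AE count in that report is not reproducible.

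**Working it through.** No sample size, power or alpha figure is involved, and the plan states no figure to reproduce. The check compares the rules on the same events.

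**Inputs (all from Section 18.1.2).** Let R = daily routine lost, M = medical care, D = new medication, each yes or no.

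- General rule and scripted question: AE if R or M or D.
- Injury item, read under its heading: AE if M.
- Assumption: requiring medical care (injury item) is the same as seeking it (general rule).

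**Comparison for an injury caused by the care recipient.** Three yes/no triggers give 2 × 2 × 2 = 8 combinations.

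| R | M | D | General rule and question | Injury item |
|---|---|---|---|---|
| no | no | no | not AE | not AE |
| yes | no | no | AE | **not AE** |
| no | no | yes | AE | **not AE** |
| yes | no | yes | AE | **not AE** |
| no | yes | no | AE | AE |
| yes | yes | no | AE | AE |
| no | yes | yes | AE | AE |
| yes | yes | yes | AE | AE |

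The general rule records 8 − 1 = 7 combinations and the injury item records 4. They disagree on 7 − 4 = 3: routine only, medication only, and both, in each case without medical care. These are counts of combinations, not of patients or probabilities.

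**Example.** A caregiver is hurt by the care recipient, misses work, and sees no provider. A yes to the scripted question makes this an AE. Under the injury item it is not one.

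**Other text in the section.** The general AE definition covers any untoward medical occurrence and has no medical-care threshold. The moderate severity grade includes events that may interfere with daily activities and usually improve with simple measures. Both fit the three-trigger rule better than a rule resting on medical care alone.

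**The case against.** The strongest reply is that the injury item says *if*, not *only if*. The protocol does write *only if* elsewhere in the same list, for abuse or neglect of a non-participant. On that view the injury item is illustrative and the general rule still governs. This stands in part: the exclusive reading comes from the heading and the missing triggers, not from the words of the item. But if the item is illustrative, it is still ambiguous about untreated injury and still needs to be reconciled.

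Three stronger readings may tempt a reader, and the documents do not support them.

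- **That injuries go unrecorded.** The scripted question covers any new or worsening health problem whatever its cause. The text following it says that the later list adds to what the question captures. The investigator may also add events at discretion. Lost events are therefore not shown.
- **That an untreated attack is also abuse of the participant, and so an AE under another item.** That item says "Abuse/Neglect of participant: Document as adverse event per above protocol", with no medical-care condition. But nothing defines abuse or says that an attack by a person with dementia falls under it, and aggression by the care recipient is handled separately.
- **That the note makes every injury an AE.** Saying that other behaviors without injury are not AEs does not imply that every injury is one. The note is silent on an injury that needs no medical care.

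It is also fair to say that the disputed group is narrow. A prescribed medication usually means that care was sought, so the medication trigger adds mainly medicines that the caregiver buys without a visit. Finally, planned follow-up should be over: Section 5.1 gives 12/1/2021 as the end of Phase II recruitment and of consents to the waitlist extension, each with six months of follow-up, and the latest revision is dated 4/28/23. That removes most of the value of retraining staff, but not of a single rule for classifying events already reported.

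**Conclusion.** The concern holds as a narrow inconsistency. Read under its heading, the injury item makes an injury without medical care a non-AE even when it stops the daily routine or leads to a new medication. The general rule and the scripted question make the same injury an AE. The disagreement covers three of eight trigger combinations.

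This rests on two assumptions: that the heading makes the medical-care condition the sole exception, and that requiring care equals seeking it. If required care is judged more narrowly than sought care, the rules also differ for caregivers who sought care that was not thought necessary. The number of participants affected cannot be derived. The fault concerns the consistency of safety reporting; sample size, power and efficacy analyses are untouched.

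**What to change.** Reconcile the scripted question, the general rule and the injury item in Section 18.1.2. Move the injury item into the list of events considered AEs, and replace its separate medical-care condition with the three triggers already stated there. This brings the item into line with the rest of the section and adds no new threshold. Then apply that one rule to the events already reported when the safety summary is compiled.

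The note on behaviors without injury can stay as it is. Recording attacks without injury under the abuse/neglect item should not be part of the change: it would be a new reporting policy and would conflict with that note.

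The cost is a wording change, a recheck of how a few reported events were classified, and possibly a few more recorded AEs.

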18.1.3 Protection Against Study Risks

Informed consent process. In creating our research design and sampling procedures, an important objective was to preserve the privacy, confidentiality, and autonomy of all participants. Following discussion of the Phase I or Phase II components to potential caregivers, the research coordinator or research assistant will reach out to the caregiver.

Inclusion criteria are as follows: 1) The care recipient has a physician diagnosis of Alzheimer's disease or a related dementia (ADRD); and 2) the caregiver is 21 years of age or older; 3) English-speaking 4) self-identifies as someone who provides help to the person with ADRD because of their cognitive impairments, 5) indicates a willingness to

PROTOCOL TITLE: Care to Plan: Preliminary Efficacy of a Tailored Resource for Family Members of Persons with Dementia

use Care to Plan (CtP), and 6) caregiver resides in one of 4 Riverside Health regions (based on zip code).

During the informed consent process, the research coordinator or research assistant will explain the project in detail to each potential participant, including a description of the types of assessments to be obtained and the time required. The UMN study coordinator or research assistant will read the telephone-based consent form and the caregiver will have the opportunity to ask questions. If the consent form is mailed in hard copy or e-mailed on request: the study staff provide a project overview, the individual has the ability to review the consent form via mail/email, and then the study staff provide the opportunity to ask any questions prior to obtaining/completing the verbal telephone consent to complete the final pages of the form (*note: in cases of participants requesting a hard copy/e-mail copy of the consent form prior/during, the consent script is not read verbatim by study staff unless a participant were to request this.*) The electronic version of the consent form will be signed by the member of the study team reviewing consent with the participant ([name], research coordinator, or research assistant). Participants will be mailed/mailed a copy of the completed consent form for their records. Please note: An additional permission form will be required for those opting to enroll in the post-Phase II waitlist control.

Additional protection against risks. Those who endorse a history of a serious mental health disorder whose: a) symptoms have exacerbated in the last six months, and b) are not receiving steady, ongoing pharmacological or other treatment for these symptoms, will be excluded from our project. The experience of the research team and the exclusion of caregivers with serious psychiatric illness will minimize the possibility of psychological risks. The unlikelihood of such problems is evident from the absence of any clinically significant problems during the past 13 years that the research team has operated various protocols related to dementia caregiving intervention research.

18.2.0 INTERIM ANALYSIS

Interim analyses are not planned because this is an R21 project that is largely designed to establish the feasibility and potential efficacy of CtP to inform a larger, subsequent randomized controlled trial.

18.3.0 DATA AND SAFETY MONITORING

18.3.1 Frequency of Data and Safety Monitoring

In addition to ongoing review of the protocol and human subjects research compliance during weekly project meetings with staff, the PI ([name]) will generate annual reports to ensure that each case complies with Institutional Review Board (IRB) requirements, including use of IRB-approved forms (particularly the consent form), and that each staff person on the proposed project adheres to the study protocol. In both weekly meetings and audit reports, [name] will actively work with project staff to minimize research-associated risk and protect confidentiality of participant data (see

PROTOCOL TITLE: Care to Plan: Preliminary Efficacy of a Tailored Resource for Family Members of Persons with Dementia

Protection of Human Research Subjects section). The research staff will be trained to interview in ways that are non-threatening, friendly, and respectful. We will emphasize to all participants that they do not have to complete any question they do not want to answer, and that the interview may be terminated at any time according to their wishes. We will stress to ADRD caregivers that their decision to discontinue the study will in no way affect the services they are receiving from the University of Minnesota, RHS or other entities. . The Safety Officer will act in an advisory capacity to the NIA PO to monitor participant safety, evaluate the progress of the study, to review procedures for maintaining the confidentiality of data, the quality of data collection, management, and analyses.

In the event a caregiver does become upset during the interview process, the research staff will contact [name], who will be available for consultation. If a caregiver is in crisis because of their care situation or some other reason, research staff will be instructed to consult with [name]. With the caregiver's permission, we will then refer the participant to the appropriate resource person in an external agency (e.g., the Alzheimer's Association). Based on the research team's experience working with their caregiving families, we expect very few or no such instances to occur. If a member of the research team does identify neglect or other potentially inappropriate care practices, the Virginia Adult Protective Services will be notified to protect the rights of persons with dementia and their families.

All information obtained from the participants will remain strictly confidential and will not be released except at the express written request of the study participant. All electronic data will be maintained on the secure Academic Health Center project folder, the Secure Computing Environment, as well as within the secure Box and Qualtrics applications. All data on [name] computer in [name] and the research staff's computers (also located in [name]) are encrypted and protected by strong passwords only accessible to [name] and the research team. The data will be maintained on the Academic Health Center secure project folder for approximately 2-3 years which is the time anticipated it will take to disseminate any and all research papers or presentations from these data. Similarly, paper forms of the data will be located in a locked file cabinet in [name] only accessible to the research team. Unless the data are being filed or accessed, these cabinets will remain locked. Staff working remotely will continue use of these secure environment's as needed.

Note: University staff calling from personal lines outside of the University will block their personal numbers when able, note they are calling from a personal line to reduce and request a callback to a work-based telephone number, or use a google voice account. Riverside staff will adhere to their internal agency policies.

Annual reports. The responsibility of [name] (who has oversight for the data management and analysis of the project), along with study staff, will include the

PROTOCOL TITLE: Care to Plan: Preliminary Efficacy of a Tailored Resource for Family Members of Persons with Dementia

production of an annual report that will highlight the results of the audit analysis, as well as study progress. In addition, [name] and study staff will provide information on any deviations from the approved protocol (e.g., deviations in adhering to study eligibility criteria), error rates, and any other issues related to the progress of the study. The Safety Officer will review the annual report to ensure ongoing quality control, and will work with [name] and the study staff, if needed, to ascertain if audited cases deviate from the approved study protocol. In instances of adverse events occurring, the procedures in the protocol will be followed.

The Safety Officer will review study progress, data quality, and participants safety at a predetermined intervals (e.g. annually) and make recommendations to the NIA for or against the trial's continuation, as well as any modification to the study. Safety reports will be distributed to the Safety Officer annually and will include a detailed analysis of study progress, data and safety issues.

Data will be compiled by the graduate research assistant or other study staff, and if greater expertise is required, by a statistician ([name]) in the University of Minnesota Medical School. All data will be directly available to the Safety Officer and the NIA Program Officer on request.

When final research results are generated, the research team may share any publications derived directly with research participants.

18.3.2 Content of Data and Safety Monitoring Report

The annual report will include the following:

1. Title Page
2. Table of contents
3. Report summary
 - a. Protocol synopsis
 - b. Discussion of issues or problems
 - c. Report preparation procedures
4. Study description
 - a. Project organizational chart, personnel
 - b. Brief statement of purpose of trial
 - c. Projected timetable and schedule
 - d. Overall study status
5. Study recruitment and administration
 - a. Reasons for screen failures
 - b. Enrollment by year or month of study
 - c. Comparison of target to actual enrollment by month
 - d. Demographic and key baseline characteristics
 - e. Withdrawals
 - f. Forms status

PROTOCOL TITLE: Care to Plan: Preliminary Efficacy of a Tailored Resource for Family Members of Persons with Dementia

- i. Status of forms (e.g., consent, completing of screener, baseline assessment, etc.)
- g. Summary of protocol changes
- h. Summary of reportable information/adverse events [safety assessment]
 - i. Adverse events
 - ii. Serious Adverse Events
 - iii. Deaths
 - iv. Protocol deviations
- 6. Action items (as needed)

